1 STUDY DETAILS

1.1 Study Objectives

To compare the performance of the M4 prediction model (M4) with the hCG cut-offs recommended by NICE (1, 2), (hereafter referred to as the protocols), when used as part of a clinical management algorithm for women with a pregnancy of unknown location (PUL). The psychological impact on subjects managed as PUL will be studied with a self-reporting scale (HADS) and a questionnaire, which will be presented in a complementary SAP in due time.

1.1.1 Primary objective (*Diagnostic performance of the protocols*)

To determine the protocols' ability to correctly categorise an ectopic pregnancy (EP) as high risk (sensitivity) and categorise a non-ectopic pregnancy (failed PUL or intrauterine pregnancy (IUP)) as low risk (specificity).

1.1.2 Secondary objective

- To evaluate the safety and effectiveness of the protocols based on clinical outcomes (see clinical variables 3.9.2).
- To investigate if ectopic pregnancies correctly categorised as high risk and non-ectopic pregnancies correctly categorised as low risk benefit in regard of safety and effectiveness in comparison with those incorrectly categorised.

1.2 Study Design

This study is a multicentre randomised comparative diagnostic and clinical impact trial of two hCG-based protocols for PUL management. The study has a superiority design regarding the primary outcome of specificity for non-ectopic pregnancies for M4, given that the primary outcome of sensitivity for ectopic pregnancies is not inferior (non-inferiority design) in comparison with hCG cut-offs recommended by NICE. The diagnostic performance of the protocols will be evaluated on all subjects as a cross-sectional study for the primary analysis as well by randomisation groups in a sensitivity analysis.

[figure not shown]

1.4 Sample Size

1.4.1 Original sample size calculation

The sample size calculation was based on data from our previous study where M4 and the hCG cut-offs by NICE had a sensitivity of 89% and 86% for ectopic pregnancy respectively ($p=0.42$) (3). The specificity for non-ectopic pregnancy (IUP and failed PUL) was 78% and 70% respectively for M4 and the hCG cut-offs ($p=0.01$) (3).

The primary objective to test the superiority of M4 compared with NICE in specificity for non-ectopic pregnancies with 80% power. A reference specificity of 70% (NICE) is used. Considering eight percentage points to be a clinically important difference in specificity, given $\beta=20\%$, $\alpha=5\%$ and a two-sided test, 495 patients are needed per group to demonstrate superiority.

STATISTISKA KONSULTGRUPPEN		Statistical Analysis Plan
Protocol: Management of pregnancies of unknown location- a randomised controlled trial of two hCG-based decision support models.	Version: 1.0	Page 8 of 18

The primary objective will also test the non-inferiority of M4 to NICE in sensitivity for ectopic pregnancy. A reference sensitivity of 86% (NICE) is used and we would allow a one percentage point lower sensitivity for M4 and that the lower limit of the two-sided 95% CI for the difference between the two protocols should not exceed seven percentage points with a probability of 80% ($\beta=20\%$), to be a non-inferior difference. Given a significance level (α) of 5% and a two-sided test, 541 patients per randomisation group are needed.

In our previous study five percent of patients were lost to follow-up, while another study reported a 7% loss to follow-up [46]. We have estimated the maximum rate of loss to follow-up to be 10%. For protection against that 10% of patients will be lost to follow-up, a total of approximately 1200 patients are needed.

1.4.2 *Cross-sectional sample size calculation*

No sample size calculation was performed a priori. A post-hoc power analysis will be performed.

1.4.3 *Secondary outcomes*

No sample size calculation was performed for secondary outcomes.

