4.9 Efficacy Analyses

4.9.1 Primary Efficacy Analysis

Diagnostic performance will be described with sensitivity, specificity, positive predictive value (PPV) and negative predictive value (NPV), positive and negative likelihood ratio (LR+, LR-). The sensitivity represents ectopic pregnancies (EP) and persistent PUL correctly categorised as high risk of being an EP and the specificity represents non-ectopic pregnancies (IUP and failed PUL) correctly categorised as low risk of being an EP. PPV represents EP among PUL categorised as high risk and NPV represents IUP and failed PUL among PUL categorised as low risk.

The primary analysis will be performed for both M4 and NICE protocols on cross-sectional data for all subjects in the FAS population. To test differences in sensitivity and specificity between M4 and NICE the sign test will be used.

In addition to the cross-sectional analysis above a sensitivity analysis will be conducted to test differences in diagnostic performance measures by randomised groups for the FAS population. An exact 95 % CI will be calculated for the difference in sensitivity between the groups. The same will be produced for the specificity.

Complementary analyses will also be conducted for the per-protocol population.

Summary of all primary variables will also be presented totally and by randomised groups and by risk category (seven columns) as described in general methods above. This will be made for both FAS and per-protocol population.

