6 CHANGES OF ANALYSIS FROM ORIGINAL STUDY PROTOCOL

The primary analysis will be performed for both M4 and NICE protocols on cross-sectional data instead of by randomised groups as stated in the original study protocol. As diagnostic performance is the primary outcome, we reasoned that a cross-sectional design would better utilise the reached sample size and maintain sufficient power, than the originally planned randomised design. Instead, the randomised groups are used in a sensitivity analysis of the diagnostic performance. This change from the original study protocol has been made before lock and analysis of the database. The randomised design is kept for the secondary clinical outcomes.

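### The 541 and 495 per group in SAP 1.4.1 are counts of ectopic and non-ectopic pregnancies, not of all randomised women, so about 1200 does not give 80% between-group power for both primary outcomes; the power of the paired primary analysis is asserted without a calculation

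*SAP*

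**What the plan says.** Section 1.4.1 makes two calculations. For superiority in specificity (78% against 70%, two-sided 5%, 80% power) it finds that "495 patients are needed per group to demonstrate superiority". For non-inferiority in sensitivity it states: "A reference sensitivity of 86% (NICE) is used and we would allow a one percentage point lower sensitivity for M4". With a margin of seven points and 80% power, it concludes that "541 patients per randomisation group are needed". After an allowance for 10% loss to follow-up, "a total of approximately 1200 patients are needed". No EP proportion appears anywhere in the calculation.

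Section 4.9.1 defines the two measures on different women. For the first measure it says: "The sensitivity represents ectopic pregnancies (EP) and persistent PUL correctly categorised as high risk of being an EP". The second measure is confined to the remaining women, who have neither an EP nor a persistent PUL: "the specificity represents non-ectopic pregnancies (IUP and failed PUL) correctly categorised as low risk of being an EP". Under section 2.1.1 the full analysis set contains all of these outcomes together.

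The primary analysis is now a paired, cross-sectional comparison of both protocols in all women, and the comparison by randomised group is kept as a sensitivity analysis. Section 1.4.2 says that no calculation was made in advance for the paired analysis and adds: "A post-hoc power analysis will be performed". Section 6 nevertheless justifies the change on the ground that the cross-sectional design "would better utilise the reached sample size and maintain sufficient power" than the randomised one.

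**The concern.** A woman contributes either to sensitivity or to specificity, never to both. A requirement for sensitivity is therefore a number of EPs, and a requirement for specificity is a number of non-EPs. To convert either into a number to randomise, it must be divided by the share of women of that kind. Section 1.4.1 skips this step and treats both figures as counts of all randomised women.

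Section 1.2 makes the superiority claim on specificity conditional on non-inferior sensitivity, so the outcome with the smaller denominator (at any EP proportion below one half) is the gatekeeper. The by-group comparison remains a planned analysis with its own tables (14.2.2.1 and 14.2.2.2), and 1.4.1 is the only power statement it has. An inconclusive by-group result for sensitivity would be read against 80% power that the design did not have. For the primary analysis, sufficient power is part of the stated reason for changing the design, yet nothing in the SAP shows it.

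**Working it through.** **Reproducing the plan's figures** (inputs from 1.4.1)

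- Sensitivity, 85% v 86%, margin 7 points, so 6 points to spare: n = (1.960 + 0.8416)² × (0.86×0.14 + 0.85×0.15) / 0.06² = 540.5, i.e. 541 per group. Exact match.
- Specificity, 78% v 70%, pooled-variance two-proportion formula: 470.7 per group; with continuity correction 495.4. The SAP has 495.
- Total: 541 × 2 / 0.9 = 1202, i.e. about 1200. Conversely, 1200 × 0.9 / 2 = 540 evaluable per group.

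Each formula is right. The fault is the population to which the results are applied.

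**Check that needs no EP proportion**

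541 EP + 495 non-EP = 1036 evaluable per group, against about 540. Even 1036 is enough only if the EP share happens to be 541/1036 = 52%. With the uncorrected 471 the sum is 1012, and the conclusion is the same.

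**Between-group power at 540 evaluable per group** (EP proportion assumed)

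Non-inferiority power = Φ[(d + 0.07) / √((pM(1−pM) + pN(1−pN)) / nEP) − 1.96], where pM and pN are the sensitivities of M4 and NICE, d = pM − pN and nEP = 540 × EP proportion. Specificity power uses 540 × (1 − EP proportion).

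| EP proportion | EP per group | NI power, 85% v 86% | NI power, 89% v 86% | Non-EP per group | Specificity power, uncorrected / corrected | Evaluable total for 80% on both |
|---|---|---|---|---|---|---|
| 10% | 54 | 14.1% | 35% | 486 | 81% / 79% | 10,820 |
| 20% | 108 | 24.0% | 60% | 432 | 77% / 74% | 5,410 |
| 30% | 162 | 33.5% | 78% | 378 | 71% / 68% | about 3,610 |

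The last column is 2 × max(541/p, 495/(1−p)), with p the EP proportion. The 89% v 86% column uses the sensitivities that 1.4.1 cites from the previous study. Over all EP proportions, the lower of the two powers (specificity uncorrected) peaks at 53% (at 53% EP) on the planned effects, and at 73% (at 27% EP) with 89% v 86%.

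**Paired analysis with 1080 evaluable in total** (EP proportion and discordance assumed)

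Non-inferiority power = Φ[(d + 0.07) / √((disc − d²)/nEP) − 1.96], where disc is the proportion of EPs that the two protocols classify differently and nEP is now the total number of EPs. With the planned d = −0.01:

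| EP (share of 1080) | NI power, 5% to 20% discordance | 95% CI half-width, points |
|---|---|---|
| 108 (10%) | 80% to 29% | 4.2 to 8.4 |
| 216 (20%) | 98% to 50% | 3.0 to 6.0 |
| 324 (30%) | over 99% to 68% | 2.4 to 4.9 |

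EPs needed for 80% power, (1.960 + 0.8416)² × (disc − d²) / (d + 0.07)²: 109, 218, 262, 327 and 436 at 5, 10, 12, 15 and 20% discordance, which is 10% to 40% of 1080. If M4 is truly 3 points better, 39 to 157 EPs suffice over the same range.

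Paired specificity power for an 8-point difference, Φ[(0.08√n − 1.96√disc) / √(disc − 0.08²)], is lowest at 756 non-EP and 40% discordance, where it is 93.7%. Elsewhere over 756 to 972 non-EP and 10% to 40% discordance it is higher.

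**The case against.** The strongest reply is that 1.4.1 is history. Its heading says so, the paired analysis has replaced it as primary, section 6 speaks of a sample size already reached, and no estimate or decision rule depends on 541 or 495. That limits the remedy to wording and a short calculation. It does not make the figures right, because the by-group comparison is still planned and has no other power statement.

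Second, the section 6 sentence is partly comparative: the cross-sectional design is said to do better than the randomised one. The figures support that; at 10% EP, paired non-inferiority power is 29% to 80% against 14% between groups. For specificity, the word sufficient is probably also correct. What remains open is whether power is sufficient for non-inferiority of sensitivity.

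Third, section 4.9.1 attaches no non-inferiority rule to the by-group interval and gives the paired analysis only a sign test. The first point softens the harm from the by-group analysis, since a wide interval shows its own imprecision. The second means that the paired power above is for an interval-against-margin procedure that 4.9.1 does not spell out. Section 1.2 nevertheless keeps the non-inferiority condition, so precision against the margin is the relevant quantity.

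Fourth, 1.4.2 does not say that observed effects will be used. That is fair: with planned effects and actual counts, the promised analysis would come close to what is needed. With observed effects it would add nothing to the p-value.

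**Conclusion.** The concern holds. The claim of 80% between-group power for both outcomes is wrong at every EP proportion, on the SAP's own inputs. At EP proportions of 10% to 30% the shortfall is mainly in sensitivity: about 14% to 33.5% power if M4 is one point worse as planned, and 35% to 78% even if it is three points better. Specificity falls short by much less, at 81% to 71% uncorrected.

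For the paired primary analysis, sufficient power is unsupported, not shown to be false. Specificity power looks high (about 94% or more over the range tried). Non-inferiority power runs from 29% to over 99% at the planned one-point deficit.

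EP proportion, discordance and the evaluable numbers (540 per group, 1080 in total, from 1200 less 10%) are assumptions; the SAP gives no EP proportion, discordance or reached sample size. All power figures are normal approximations. The finding that both targets cannot be met rests on none of the assumed EP or discordance values. This should be corrected before the analysis, because it concerns the stated power of a gatekeeping outcome and the stated reason for replacing the primary analysis.

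**What to change.** - **Section 1.4.1:** keep 541, 495 and 1200 as the record. Add a note that 541 is the number of EPs (including persistent PUL) per group, that 495 is the number of non-ectopic pregnancies per group, and that about 1200 women do not give 80% between-group power for both outcomes. State the between-group power over a given range of EP proportions.
- **Section 1.4.2:** replace the post-hoc power analysis with a paired calculation made before the analysis. It should use the planned effects, not the observed ones; the expected or reached numbers of EP and non-EP; a stated range of discordance; and the expected confidence interval width for the difference in sensitivity, set against the seven-point margin.
- **Section 6:** support the statement on sufficient power with that result, separately for sensitivity and specificity, or delete it.

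No additional enrolment is needed, and test, population and margin do not change. The cost is a few sentences and a short calculation; the only downside is a less favourable stated power.

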4 STATISTICAL METHODOLOGY

4.1 General Methodology

Descriptive statistics will be presented by mean, standard deviation (SD), median, Q1 and Q3 (continuous variables) and number and percentage (categorical variables).

All tests will be two-tailed and conducted at the 0.05 significance level. All analyses will be performed by using SAS® v9.4 (Cary, NC).

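### The power of the new cross-sectional primary analysis is asserted without a figure, and the only planned check is an unspecified post-hoc power analysis; the gap matters for sensitivity non-inferiority

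*SAP*

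**What the plan says.** Section 1.4.1 sizes the trial for two independent randomised groups: 495 per group for superiority in specificity (70% against 78%), 541 per group for non-inferiority in sensitivity (86% against 85%, 7-point margin), and about 1200 in all after 10% loss to follow-up.

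Section 6 then moves the primary analysis to cross-sectional data on all women, on the reasoning that "a cross-sectional design would better utilise the reached sample size and maintain sufficient power, than the originally planned randomised design". On timing it adds: "This change from the original study protocol has been made before lock and analysis of the database." No power figure is given.

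For this new primary analysis, section 1.4.2 says only: "No sample size calculation was performed a priori. A post-hoc power analysis will be performed."

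Section 4.9.1 gives the test: "To test differences in sensitivity and specificity between M4 and NICE the sign test will be used." The exact 95% CIs in that section are described in the paragraph on the randomised groups, not for the paired comparison.

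**The concern.** Power is the reason given for changing the primary analysis, so a reader will want to see it. The calculations in 1.4.1 cannot serve. They are for independent groups, whereas the power of a paired comparison depends on how often M4 and NICE disagree on the same woman, which the SAP never states. Sensitivity is also estimated only in EP (with persistent PUL counted as EP, section 3.9.1), and their expected number is not given either.

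A post-hoc analysis with no inputs named does not fill the gap. If it takes the observed effect, it carries no information beyond the p-value. For sensitivity it can mislead: the closer M4 is to NICE, the better for non-inferiority, but the lower the observed power of a test of no difference. The report could then carry a figure that looks like validation of the design, or a criticism of it, and is neither.

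**Working it through.** **1. The plan's own figures reproduce.**
- Sensitivity: n = (1.960 + 0.842)² × (0.86×0.14 + 0.85×0.15) / (0.07 - 0.01)² = 7.849 × 0.2479 / 0.0036 = 540.5, so 541 per group, as stated.
- Specificity, 70% against 78%: 471 per group without and 496 with continuity correction; 495 is stated.
- Total: 2 × 541 / 0.90 = 1203; about 1200 is stated.

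All three are independent-groups results.

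**2. Power at the observed effect.** For a two-sided test at 0.05 with observed statistic z, observed power = Φ(|z| - 1.96) + Φ(-|z| - 1.96). This depends only on p:

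| p | observed power |
|---|---|
| 0.01 | 73% |
| 0.05 | 50% |
| 0.20 | 25% |
| 0.42 | 13% |
| 0.50 | 10% |

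The exact sign test behaves alike: 60 against 40 discordant pairs gives p=0.057 and plug-in power of about 46%. The row p=0.42 is the p-value that 1.4.1 reports for sensitivity in the previous study, where M4 was 3 points better (89% against 86%).

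**3. Example for sensitivity.** Assume 216 EP, an observed difference of -1 point and 10% discordance.
- SE = √((0.10 - 0.01²)/216) = 0.0215.
- 95% CI = -0.010 ± 1.96 × 0.0215 = -5.2 to +3.2 points, inside the 7-point margin.
- |z| = 0.010/0.0215 = 0.465, so observed power = Φ(-1.495) + Φ(-2.425) = 0.067 + 0.008, about 7.5%.

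**4. Prospective paired power, sensitivity.** True difference -1 and margin 7 come from 1.4.1. Assumptions: 1080 evaluable women (1200 × 0.90), EP share 10-30%, discordance ψ among EP. Power = Φ(0.06/√((ψ - 0.0001)/n) - 1.96).

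| EP share (n) | ψ=5% | ψ=10% | ψ=20% | randomised groups |
|---|---|---|---|---|
| 10% (108) | 80% | 51% | 29% | 14% |
| 15% (162) | 93% | 68% | 40% | 19% |
| 20% (216) | 98% | 80% | 51% | 24% |
| 30% (324) | >99% | 93% | 68% | 34% |

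The last column splits 541 women per group by the same EP share: power = Φ(0.06/√(0.2479/m) - 1.96) with m = 541 × share. For 80% power, the paired analysis needs 109, 218, 327 and 436 EP at ψ = 5, 10, 15 and 20%.

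**5. Prospective paired power, specificity.** The difference is 8 points. Power = Φ((0.08√n - 1.96√ψ)/√(ψ - 0.0064)). The least favourable case in the assumed range is 30% EP, leaving n = 1080 × 0.70 = 756, with ψ = 38.8%, the value if the two protocols were independent (0.70×0.22 + 0.30×0.78). There, power = Φ((2.200 - 1.221)/0.618) = Φ(1.58), about 94%. For 80% power, 121, 182, 243, 366 and 474 non-ectopic women are needed at ψ = 10, 15, 20, 30 and 38.8%.

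**The case against.** Three stronger readings are tempting, and the SAP supports none of them.

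- *The post-hoc analysis will follow the results and merely restate p.* Section 1.4.2 states neither the effect nor the timing. Set against the reached sample mentioned in section 6, it could mean power at that sample for the design values in 1.4.1. Such a calculation does not restate p: with 900 non-ectopic women and 100 discordant pairs, power for 8 points is near 100% whether the pairs split 55/45, 60/40 or 65/35. The observed-power argument is therefore conditional.
- *The switch has no support.* Section 6 largely makes a comparison with the randomised design, and that comparison holds: paired power exceeds randomised power in every scenario above, and specificity is well covered. Only the sufficiency of power lacks a figure, and the doubt is about sensitivity.
- *A trial meeting its margin would be called underpowered.* It could be, if the analysis used the observed effect in a test of equality and were read that way. The SAP does not say so.

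It is also fair to say that a power statement changes no estimate or test, and that at 5% discordance power for sensitivity is 80% or more. What stands is that the SAP offers no way to tell which case applies, and leaves the one planned check undefined.

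**Conclusion.** The point holds as a gap in justification and specification. Power is the stated reason for changing the primary analysis, it is not quantified, and the planned post-hoc analysis has no inputs. For specificity the reasoning in section 6 is sound: about 94% or more over the assumed range. For sensitivity non-inferiority, power may be anywhere from 29% to over 99%, depending on the number of EP and on discordance among them. Evaluable number, EP share and discordance are assumptions, since the SAP gives none for the reached sample. The estimates themselves are unaffected; what suffers is the rationale for the switch and a figure that may be reported and misread.

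**What to change.** - Delete the post-hoc power analysis from 1.4.2.
- Before analysis, put in its place a paired calculation at the SAP's own design values: true difference -1 and margin 7 for sensitivity, 8 points for specificity. Use the reached numbers of EP (including persistent PUL) and of non-ectopic women, and a stated range of discordance given separately for the two. A pooled discordance rate would be the wrong input for sensitivity.
- In section 6, replace the general claim of adequate power with that figure.
- In 4.9.1, plan paired 95% CIs for both differences, and read the results against the 7-point margin and the 8-point difference.

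The cost is one short calculation and a few lines of SAP text. The downside is that the stated power for sensitivity may turn out below 80%.

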2 STUDY POPULATIONS

2.1 Definition of Study Populations

2.1.1 *Full Analysis Set*

All randomised subjects with a known outcome of PUL (IUP, failed PUL or EP) are included in the Full Analysis Set (FAS).

2.1.2 *Per protocol population*

All subjects included in FAS that were followed-up according to categorisation in high or low risk and that were managed according to the corresponding algorithm. Subjects deviating from the algorithm are not included in the per-protocol population. The per-protocol population is used for analyses of secondary outcomes.

